5.2.5 Hepatotoxicity

In general, guidelines established for imatinib use in CML and GIST will be followed,^{129,130} but a more conservative approach will be used, as follows. Liver function tests (LFTs) will be obtained every other week during the first month of therapy, and monthly thereafter.

For grade-2 transaminase (ALT or AST $> 3.0 \times \text{ULN}$) or bilirubin ($> 1.5 \times \text{ULN}$) elevations, imatinib must be suspended, and the LFTs monitored weekly. When they have fallen to grade 1 or normalized, imatinib will be restarted at 50% of the initial daily dose. If the liver toxicity does not recur within 6–12 weeks, then the initial dose will be restored. If after resumption of treatment grade 2 transaminase or bilirubin elevations recur, study drug will be permanently discontinued.

For grade-1 abnormalities (ALT or AST greater than or equal to $1.0\text{--}3.0 \times \text{ULN}$; bilirubin greater than or equal to $1.0\text{--}1.5 \times \text{ULN}$), imatinib treatment can be continued but LFTs will be monitored weekly for 2 weeks and then, if no worsening is observed, every other week. Concomitant hepatotoxic agents, such as alcohol or acetaminophen, should be removed. Persisting grade 1 abnormalities should be managed by dose reduction, biweekly monitoring, and further evaluation in conjunction with gastroenterology consultation.

5.2.6 Myelosuppression

In general, recommendations will be a conservative algorithm, derived from Deininger et al. for the chronic phase of CML will be followed.¹²⁹ For grade 1 neutropenia (absolute neutrophil count [ANC] $< \text{LLN-}1500/\text{mm}^3$) and thrombocytopenia ($< \text{LLN-}75,000/\text{mm}^3$), the dose of imatinib will be reduced to 50% of the initial dose. Counts will be monitored bi-weekly. The initial dose will be restored when myelosuppression resolves.

For grade 2 or greater events (ANC less than $1,500/\text{mm}^3$, or platelets less than $50,000/\text{mm}^3$) imatinib should be suspended and the counts will be repeated weekly until they have recovered (ANC greater than $1,500/\text{mm}^3$, platelets greater than $75,000/\text{mm}^3$). For grade 1 neutrophil or platelet levels, imatinib will be restarted at 50% of the original dose, and the counts will be monitored biweekly; imatinib will be restored to the full dose when the counts normalize. If myelosuppression resolves and then occurs again at a later time, the same procedure may be followed.

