1.5.1.13 Malignancies

On-going pharmaco-vigilance data is being collected to assess risk for malignancy following imatinib exposure (see data on file, Gleevec IND 55,666). An integrated review of safety data from imatinib oncology clinical trials suggests that there may be an increased frequency of genito-urinary malignancies. However, the effect is not statistically significant, and it is limited to those subjects treated for > 2 years. Thus, we will exclude any subjects with prior malignancy, and will carefully monitor genito-urinary risk throughout the study with serial urinalyses and prostate specific antigen (for male participants)

When rats are treated with imatinib for 2 years, they had a shortened lifespan, and higher risk for developing cancers in the kidneys, bladder, urethra, clitoris, small intestine, parathyroid glands, adrenal glands, and stomach. The relevance of these findings to humans is not known.

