15. Any sign of QT prolongation on Visit -1 ECG (> 450 ms in males and > 470 ms in females).
16. Known coagulation disorders or use of anticoagulants
17. Current and anticipated on-going treatment with drugs that may increase or decrease imatinib plasma concentrations (CYP3A4 family inhibitors or inducers) or drugs that may have their plasma concentration altered by imatinib (drugs metabolized by CYP3A4/5 and CYP2D6).
18. Any condition that, in the investigator's opinion, may compromise study participation or may confound the interpretation of the study results.

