5.2 DOSE MODIFICATION AND MANAGEMENT OF ADVERSE EVENTS

With the use of a relatively low dose of imatinib in an otherwise healthy population, we hope to minimize the nature and extent of AEs experienced. It is important to note here, as in section 1.4, that the AEs referenced below, if observed, will usually occur early in the course of treatment, are often self-limited, and do not usually require dose adjustment or discontinuation of imatinib. Nonetheless, the investigative team recognizes that cancer treatment is clearly different than the proposed elective clinical trial: side effects considered acceptable and tolerable in a cancer setting may not be considered in the same light for subjects in this study. Every effort will be made to carefully balance the intent to provide the maximum total prescribed dose of study drug to subjects, versus the discomfort and risk that may be accompanied with imatinib administration. The “art” of subject management in this study will be to minimize the number of subjects that drop out of the trial due to these side effects, working in close concert with the investigative team to either adjust study drug dose and/or provide symptomatic relief with concomitant medications. General guidelines are outlined below, but may need to be modified as deemed necessary, in consultation with the trial physicians and medical monitor. In general, when a dose reduction is required, the daily dose of imatinib or placebo will be halved: For adults, the dose will be reduced from

400 mg/day to 200 mg/day. Unless otherwise stated, the equivalent dose reduction in children will be from 260 mg/m²/day to 130 mg/m²/day. Investigators will be instructed to always round up to the nearest 50 mg increment for the half-dose dosage.

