6.2 RANDOM ASSIGNMENT, BLINDING, AND UNBLINDING

6.2.1 Random Assignment

Participants who sign the informed consent and meet the eligibility criteria will be randomly assigned in a 2:1 ratio to either the experimental or control group. A central automated randomization system will be used for treatment assignment and to create a unique identifier for each new study participant. Random assignment will be stratified according to site.

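### The platelet count that triggers suspension in 5.2.6 does not meet that section's grade 1 limit, and the prior-malignancy exclusion stated in 1.5.1.13 is missing from the eligibility lists

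*Combined protocol and SAP*

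**What the plan says.** **Platelets.** Section 5.2.6 sets two levels of response. For grade 1 the action is a half dose with bi-weekly counts: "thrombocytopenia ($< \text{LLN-}75,000/\text{mm}^3$), the dose of imatinib will be reduced to 50% of the initial dose". For anything worse the drug is stopped and counts are repeated weekly: "For grade 2 or greater events (ANC less than $1,500/\text{mm}^3$, or platelets less than $50,000/\text{mm}^3$) imatinib should be suspended". Recovery after suspension requires platelets above 75,000/mm³. The parent section 5.2 describes its rules as adaptable: "General guidelines are outlined below, but may need to be modified as deemed necessary".

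**Prior malignancy.** Section 1.5.1.13 reports a possible excess of genito-urinary cancers in the oncology trials and concludes: "Thus, we will exclude any subjects with prior malignancy". The same sentence promises serial urinalysis and, for men, prostate-specific antigen. Section 6.2.1 makes the eligibility criteria the gate to the trial: "Participants who sign the informed consent and meet the eligibility criteria will be randomly assigned in a 2:1 ratio". The only exclusion in 4.2 that could reach prior malignancy is criterion 18, which covers conditions that, in the investigator's judgement, "may compromise study participation or may confound the interpretation of the study results".

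**The concern.** In 5.2.6 the grade label and the printed number disagree for platelets between 50,000 and 75,000/mm³. The label points to suspension and the number does not. Two sites could treat the same count differently, and the less protective choice is the one the section's own grading does not intend.

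The missing exclusion means that a site following 4.2 exactly could randomise a person whom the protocol says will be kept out. The protection would then depend on an individual investigator's opinion, although 1.5.1.13 states it as a fixed rule.

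**Working it through.** No power or error-rate calculation applies. The check compares the printed limits and reads the eligibility lists.

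**Step 1. Where grade 1 ends and where suspension begins** (sections 5.2.5 and 5.2.6)

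| Laboratory value | Grade 1 ends at | Suspension begins at | Gap |
|---|---|---|---|
| ALT or AST | 3.0 × ULN | above 3.0 × ULN | 0 |
| Bilirubin | 1.5 × ULN | above 1.5 × ULN | 0 |
| ANC | 1,500/mm³ | below 1,500/mm³ | 0 |
| Platelets | 75,000/mm³ | below 50,000/mm³ | 75,000 − 50,000 = 25,000/mm³ |

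The liver rule shows the intended pattern, with suspension starting where grade 1 stops: "For grade-2 transaminase (ALT or AST $> 3.0 \times \text{ULN}$) or bilirubin ($> 1.5 \times \text{ULN}$) elevations, imatinib must be suspended". The neutrophil limit, in the same parenthesis as the platelet number, follows that pattern, and its recovery level is also 1,500.

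**Step 2. Individual counts under the printed rule.** At 80,000 and 75,000 the grade 1 rule applies and the dose is halved. At 74,000, 60,000 and 50,000 the count is below the grade 1 range but not below 50,000, so it matches neither printed band. Below 50,000 the drug is suspended.

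**Step 3. The same counts with a trigger of below 75,000.** Counts of 80,000 and 75,000 still lead to halving. Counts of 74,000, 60,000 and 50,000 lead to suspension. No count is left without an action.

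**Step 4. What the ambiguity means for dose and monitoring.** For an adult on 400 mg/day, a site that extends the half dose downward gives 400 × 0.5 = 200 mg/day with bi-weekly counts. A site that follows the grade label gives 0 mg/day with weekly counts. In Appendix 1, haematology during dosing falls at weeks 0, 2, 4, 9, 13, 17, 22 and 26. After week 4 the scheduled intervals are 5, 4, 4, 5 and 4 weeks. The closer rechecks in 5.2.6 start only when a band is matched, so a count in the gap has no prescribed early recheck.

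**Step 5. Eligibility lists.** Section 4.1 has 5 inclusions, none on malignancy. Section 4.2 has 18 exclusions in unbroken numbering, none on malignancy. The synopsis inclusion and exclusion lists have none either. The rest of the sentence in 1.5.1.13 did reach the schedule: urinalysis and prostate-specific antigen are both in Appendix 1. That pattern suggests an oversight more than a decision to drop the criterion.

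**The case against.** On platelets, stopping below 50,000 and restarting only above 75,000 is a coherent design, so the recovery level alone contradicts nothing. No text assigns a half dose at 60,000. The grade label and the section's stated conservative intent both point to suspension, so many investigators would reach the safer answer. Section 8.1.4 adopts CTCAE 4.0 for grading, section 8.2 sends adverse events of grade 2 or above to the coordinating center and has the medical monitor assess adverse events, and section 5.3 lets the investigator stop drug. The algorithm is derived from a cited CML management paper, so 50,000 may have been carried over on purpose and the label may be the error.

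On malignancy, the rule is in the protocol and was only left off the checklist. Section 1.5.1.13 itself says of the signal that "the effect is not statistically significant, and it is limited to those subjects treated for > 2 years", and dosing here lasts 26 weeks, a quarter of the 104 weeks in 2 years. The two points are also unrelated and could be listed separately.

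Much of this stands as a limit on consequence. The half-dose reading is an illustration of how sites might diverge and is not a printed instruction. The inferred intent of 75,000 is strong but needs the sponsor's confirmation. None of it removes the discrepancies. A stop-low, restart-high rule still leaves a participant at 60,000 who has not been suspended without a numeric action. The flexibility clause and the grading reference do not correct the printed number. Criterion 18 permits an exclusion that 1.5.1.13 requires.

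**Conclusion.** Both inconsistencies hold and should be corrected. The platelet rule leaves a band of 25,000/mm³ in which label and number conflict, and the malignancy exclusion appears in none of the lists that govern enrolment.

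The practical size is small. Entry excludes platelets below 125,000/mm³. The nearest incidence figure in the documents is grade 3 or 4 thrombocytopenia in under 1% of participants in the GIST phase II study (section 1.5.1.7). The documents give no incidence for counts of 50,000 to 75,000/mm³ and no prevalence of prior malignancy, so the view that both situations are infrequent is a judgement. The points bear on participant safety and consistent site conduct. They do not affect sample size, power, type I error or the primary analysis.

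The platelet conclusion rests on 5.2.6 alone. CTCAE cut-points are not printed in the documents and were not used.

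**What to change.** In 5.2.6, change the platelet trigger for suspension from below 50,000/mm³ to below 75,000/mm³. This agrees with the section's grade 1 limit, its recovery level, the neutrophil rule and its stated conservative aim. The sponsor should confirm the number. If 50,000 is truly intended, the text must instead assign a dose and a recheck interval to counts of 50,000 to 75,000/mm³ and correct the grade label.

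Add prior malignancy as an exclusion in 4.2 and in the synopsis.

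The cost is one number and one line in each of two lists, made in the next amendment. Medical history is already taken at screening, so there are no new visits or assays and no change to the sample size.

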Liver toxicity, if an issue, usually emerges during the first few months of therapy, but can be a late finding. Frequent monitoring of liver function is suggested during therapy. Grade 1 elevations in transaminases occur in up to 10% of treated patients and often normalize while continuing on therapy. Grade 3 events have been reported in 2%–5% of subjects in GIST and CML trials, but these events may be confounded by a variety of other factors, including leukemic liver infiltration. For grade 3 events in oncology settings, therapy is temporarily interrupted. Imatinib is permanently discontinued for grade 3 events that recur with drug re-challenge.

1.5.1.7 *Myelosuppression*

The development of myelosuppression is much more common in CML than GIST, and may relate to the underlying effects of the cancer on the bone marrow. In the phase II study of imatinib for GIST, anemia (9% of subjects, 2% grades 3 or 4), neutropenia (7% of subjects, 5% grade 3 or 4), and leukopenia (5% of subjects, 1% grades 3 or 4) were the most commonly reported findings; grades 3 or 4 thrombocytopenia was noted in <1%. Complete blood counts with differential will be monitored at the same time points as liver function tests. For myelosuppression of grade 3 or higher severity in oncology

settings, therapy is temporarily interrupted, and permanently discontinued for grade 3 events that recur with drug re-challenge.

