5.2.1 Gastrointestinal Reactions

Nausea. To minimize issues with nausea, participants will be advised to take study medication with the largest meal of the day. If the problem persists, they may need to split the study medication into twice daily dosing.

For recurrent, persistent vomiting, grades 1 and 2, lasting for 48 hours, investigators will consider the use of anti-emetics such as prochlorperazine or ondansetron. Subjects usually respond promptly, and dose reduction is seldom needed.

For grade 2 vomiting that persists for 48 hours despite the use of antiemetic drugs, imatinib will be reduced to 50% of the initial daily dose. If vomiting resolves over the ensuing week, then the full dose will be restored. If vomiting recurs, then the subject will need to remain on the 50% tolerated lower dose, and re-evaluated weekly, with return to full dose reconsidered.

For vomiting that is grade 3, or grade 2 that does not improve with anti-emetics and dose reduction for 48 hours,, imatinib will be suspended until the problem is resolved. Electrolytes should be obtained. Imatinib will then be reintroduced at 50% of the initial daily dose. If vomiting does not recur over the ensuing week, the initial dose will be restored. If vomiting of grade 3 recurs, then the drug will be permanently discontinued. If nausea or vomiting resolve and then occur again at a later time, the same procedures may be followed as outlined above, depending on the grade.

Diarrhea. If it occurs, diarrhea is often mild and requires no specific therapy. For persistent diarrhea (1 week or greater) of grades 1 and 2 the participant may be treated with antidiarrheal and antispasmodic drugs, such as Imodium®, Lomotil®, or paregoric, at the discretion of the investigator.

For grade 2 diarrhea that persists for 1 week despite the use of antidiarrheal drugs, imatinib will be reduced to 50% of the initial dose. If diarrhea improves to less than or equal to grade 1 for at least 1 week, the initial dose will be restored. If diarrhea persists despite use of antidiarrheal drugs and dose reduction, permanent discontinuation of imatinib will be considered.

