For diarrhea of grade 3 or higher, imatinib will be suspended until the problem is resolved. Electrolytes should be obtained. Imatinib will then be reintroduced at 50% of the initial dose for 1 week. If diarrhea does not recur, the initial dose will be restored. If diarrhea greater than grade 2 recurs, imatinib will be permanently discontinued. If diarrhea resolves and then occurs again at a later time, the same procedure may be followed.

Chronic diarrhea, of 14 or more days in duration, should be evaluated to determine if there is an infectious cause. Evaluation will be conducted in consultation with local infectious disease consultants, and will include a thorough clinical and epidemiological evaluation, including travel history and any possible exposures. Stool culture and other evaluation may be required, and anti-microbial therapy offered as indicated. Other potential causes of diarrhea, such as lactase deficiency, should be considered.

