5.2.2 Muscle Cramps, Bone Pain, Arthralgias

Mild to moderate cramps may respond to calcium and magnesium supplementation, and some have responded to quinine. Mild to moderate bone pain and arthralgia can usually be relieved with nonsteroidal anti-inflammatory drugs (NSAIDs) such as ibuprofen and naproxen.

For grade 2 muscle cramps, bone pain or arthralgia that persist for 1 week despite the use of symptom-relieving drugs, the dose of imatinib will be reduced to 50% of the initial daily dose. If symptoms improve to less than or equal to grade 1 for at least 1 week, the initial dose will be restored. If symptoms persist despite symptomatic treatment and dose reduction, permanent discontinuation of imatinib will be considered.

For grade 3 muscle cramps, bone pain or arthralgia, imatinib will be suspended until the problem is resolved. Imatinib will then be reintroduced at 50% of the initial dose for 1 week. If symptoms do not recur, the initial dose will be restored. If symptoms greater than grade 2 recur, imatinib will be permanently discontinued.

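### Section 5.2.6 sets no permanent stop for recurrent severe myelosuppression, so on recurrence it is weaker than the oncology rule in 1.5.1.7

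*Combined protocol and SAP*

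**What the plan says.** Section 5.2.6 describes its approach in the words "recommendations will be a conservative algorithm", derived from published guidance for chronic-phase CML. Grade 1 neutropenia or thrombocytopenia halves the dose. Everything from grade 2 upward falls into one band: suspend, check counts weekly, restart at 50% once counts are back at grade 1, and then "imatinib will be restored to the full dose when the counts normalize". The section closes with "If myelosuppression resolves and then occurs again at a later time, the same procedure may be followed". It gives no grade 3 threshold, no limit on the number of cycles and no permanent discontinuation criterion.

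The background section 1.5.1.7 describes what is done for grade 3 or worse myelosuppression in oncology "settings, therapy is temporarily interrupted, and permanently discontinued for grade 3 events that recur with drug re-challenge".

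The neighbouring rules do state a stop on recurrence. For vomiting: "If vomiting of grade 3 recurs, then the drug will be permanently discontinued". For diarrhea: "If diarrhea greater than grade 2 recurs, imatinib will be permanently discontinued". For cramps, bone pain and arthralgia: "If symptoms greater than grade 2 recur, imatinib will be permanently discontinued". Localized edema (5.2.3) and rash (5.2.4) have the same stop above grade 2, and hepatotoxicity (5.2.5) stops at a recurrent grade 2 elevation.

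**The concern.** Section 5.2 itself says that side effects accepted in cancer treatment may not be acceptable in this trial. On the first event 5.2.6 follows that intent, acting at grade 1 and grade 2. On recurrence it does not: a participant whose grade 3 or 4 neutropenia returns after re-challenge may be taken through half dose and full dose again.

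There is also a knock-on effect. The first ground for stopping drug in 5.3 is that a discontinuation criterion in 5.2 has been met, and 5.2.6 supplies none. The enrolment rule in 3.7.2.1 counts permanent discontinuations as 5.3 defines them. Recurrent severe myelosuppression therefore becomes a discontinuation, and enters that count, only through investigator judgment or participant request. Two sites could handle the same event differently.

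**Working it through.** **Comparison of the rules.** The claim rests on the text, and the plan gives no figure to reproduce.

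| Rule | What happens when a severe event recurs | Repeat procedure allowed? |
|---|---|---|
| Oncology practice, 1.5.1.7 | Permanent stop for recurrent grade 3 | Not stated |
| Vomiting, 5.2.1 | Permanent stop at grade 3 | Yes, beside the stop |
| Diarrhea, 5.2.1 | Permanent stop above grade 2 | Yes, beside the stop |
| Cramps, bone pain, arthralgia, 5.2.2 | Permanent stop above grade 2 | Not stated |
| Localized edema, 5.2.3 | Permanent stop above grade 2 | Yes, beside the stop |
| Rash, 5.2.4 | Permanent stop above grade 2 | Yes, for grade 2 only |
| Hepatotoxicity, 5.2.5 | Permanent stop at grade 2 | Not stated |
| Myelosuppression, 5.2.6 | No stop stated | Yes, any grade |

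Only the last row has the repeat permission without a stop.

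**How many participants could meet the gap.**

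Inputs:
- Imatinib arm: 44, from 2:1 allocation of 66 (66 × 2/3). Section 9.4 prints 46 + 22, which sums to 68, so 46 is used as an upper value.
- First grade 3 or 4 event: 5%, the neutropenia rate that 1.5.1.7 reports from the phase II GIST study. A low case of 1% is assumed, because 1.5.1.1 expects better tolerance here.
- Recurrence after re-challenge: not in the documents. A range of 10% to 50% is assumed.

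Expected first events = n × rate:
- 44 × 0.01 = 0.44
- 44 × 0.05 = 2.2
- 46 × 0.05 = 2.3

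Chance of at least one first event, n = 44:
- 1 − 0.99^44 = 0.357
- 1 − 0.95^44 = 0.895

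Per-participant probability of a recurrent severe event:
- low: 0.01 × 0.10 = 0.001
- high: 0.05 × 0.50 = 0.025

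Expected participants with a recurrent severe event:
- low: 44 × 0.001 = 0.044
- high: 44 × 0.025 = 1.1, or 46 × 0.025 = 1.15

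Chance of at least one such participant:
- low: 1 − 0.999^44 = 0.043
- high: 1 − 0.975^44 = 0.672, or 1 − 0.975^46 = 0.688

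**Effect on the enrolment rule in 3.7.2.1**, from this cause alone, taking the treated participants as those on imatinib:
- Two or more of the first 10, high case: 1 − 0.975^10 − 10 × 0.025 × 0.975^9 = 0.0246. Low case: 0.00004.
- The 20% rule: 0.20 × 44 = 8.8, so 9 participants would be needed, against about 1 expected in the high case.

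**The case against.** The case for leaving 5.2.6 alone has several parts.

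- **Repeat management is the protocol's usual approach.** Vomiting, diarrhea and localized edema carry a similar repeat sentence. True, but in each it sits beside a mandatory stop, and that stop is what 5.2.6 lacks.
- **The design has a rationale.** Section 1.5.1.1 calls hematological toxicity dose-dependent and reversible, and relates it largely to the underlying cancer. The comparator in 1.5.1.7 is background text, and the guidance from which 5.2.6 is derived cannot be checked from these documents. This supports halving, suspending and retrying after a first event. It does not say what to do when a severe event returns after that retry.
- **There are backstops.** The wording is permissive, 5.2 calls its rules general guidelines to be modified in consultation with the trial physicians and medical monitor, 5.3 lets the investigator stop drug for a severe event, and the DSMB reviews adverse events by arm. All of this stands, and re-challenge is not compulsory. But these controls are discretionary and apply equally to the other toxicities, for which mandatory stops were still written.
- **Repeats are limited in practice.** Dosing lasts 26 weeks, and each cycle needs recovery and normalization. Participants with ANC below 1,500 or platelets below 125,000 are excluded at entry. The 5% comes from a cancer population, and 5.2.6 intervenes earlier than the oncology practice described in 1.5.1.7. The upper figures above are therefore probably too high, and the recurrence range has no source. This limits the size of the problem but leaves the gap in the rule.
- **The platelet bands are incomplete.** Halving covers counts down to 75,000 and suspension starts below 50,000, so a falling count between the two has no stated action. That is a separate defect in the same section, and it means the claim of stricter first-event handling is clearer for neutrophils than for platelets.

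**Conclusion.** The concern holds. On recurrence of a grade 3 or higher event, 5.2.6 permits re-challenge where the oncology rule in 1.5.1.7 requires a permanent stop, and it is the only graded rule in 5.2.1 to 5.2.6 with no stop on recurrence. This is a participant-safety and consistency gap. It does not threaten the primary analysis.

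The size is small: about 0.04 to 1.15 imatinib participants, with a 4% to 69% chance of at least one. Those figures depend on the assumed 1% lower rate, on the GIST rate carrying over as the upper one, and on the assumed 10% to 50% recurrence. The conclusion about the rule itself depends on none of them. The chance that this cause alone triggers the first-10 enrolment rule is at most about 2.5%.

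**What to change.** Replace the last sentence of 5.2.6 with two sentences:

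*When grade 1 or 2 myelosuppression returns after resolving, the steps above may be repeated. If neutropenia or thrombocytopenia of grade 3 or higher (CTCAE 4.0, section 8.1.4) recurs after re-challenge, imatinib will be stopped permanently.*

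The CTCAE reference is needed because 5.2.6 has no grade 3 threshold of its own. Sections 5.2.1 and 5.2.3 need no change, since their repeat sentences already stand beside a stop.

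The cost is one short edit in one section. Blood counts are already scheduled at every visit. The downside is that roughly 0.04 to 1.15 imatinib participants would stop study drug early, but 5.3 asks them to stay in follow-up.
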